Risk Communication: Risk communication, in the form of comic books with accompanying read-along videos for the children (n=3) and videos for the parents (n=2) will be distributed in English and Spanish to all enrolled students within two weeks of completion of the ROSSEY RCT final assessment (December 2023). Three comic books will be distributed by mail and parents will be sent a password-protected link with the mailed comic to access the parent videos and comic book read-along videos. All intervention materials (i.e., children's comic books and parent videos) will be distributed after the final assessment of the larger ROSSEY RCT study is complete. The delay is to eliminate possible contamination of the RCT by siblings of comparison students who will receive the comic books as part of this ancillary study.

Outline of Early Learning Study Procedures

Follow-up Survey: We will contact parents 6 weeks after the risk communication intervention distribution. Parents will be asked to complete the follow-up survey either online or by phone. The surveys will ask for updates to their contact and demographic information, child's COVID-19 vaccination status, and child's SARS-CoV-2 mitigation behaviors and the secondary outcome measures.

Following the protocol from the ROSSEY RCT, the post assessment will take place over 6 weeks, allowing two weeks for final contact prior to closure. For EL participants with missing or phone numbers no longer in service, ROSSEY staff will contact the YSD to 1) determine if the student is still attending YSD, 2) find out school and teachers name to send a notice through the school to the parent letting them know we are trying to reach them. Students determined to still be enrolled at YSD, and are non-responders to the follow up survey, will receive an at home visit by ROSSEY staff as a final attempt to reach student and parent to complete survey. Follow-up assessment closure will take place one week after completion of home visits.

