ReOpening Schools Safely and Educating Youth (ROSSEY Study) – Early Learning Ancillary Study

Clinical Trials.gov : NCT05965323

June 30, 2022

STATISTICAL ANALYSIS PLAN

1. Introduction to the SAP

This statistical analysis plan (SAP) describes the plans for statistical analyses that will address the study's protocol objectives.

2. Study Schema and objectives

Purpose:	Evaluate if risk communication health education can increase uptake of COVID-19 mitigation measures, improve children's school attendance, and increase families' physical and mental well-being using a single-arm pre/post study.
Design:	A single-arm pre/post-study
Central Hypotheses:	Our central hypotheses are that students and parents who view the risk communications will be more likely to have increased COVID-19 testing and vaccine uptake.
Primary Objectives:	
• To determine if implementing three COVID-19 education comic books for children and two COVID-19 education videos for parents will increase COVID-19 testing and vaccine uptake in children.
Secondary Objectives:	
• To determine if implementing three COVID-19 education comics books for children and two COVID-19 education videos for parents will increase physical activity, improve sleep, increase emotional regulation in children.• To determine if implementing three COVID-19 education comics books for children and two COVID-19 education videos for parents will increase physical activity, improve sleep, decrease depression and anxiety in parents
Population:	Children ages 3-5 enrolled in the Early Learning program in Yakima School District
Study Size:	Early Learning is an ancillary study with no defined sample size. We will enroll and recruit participants for a total of eight weeks
Primary Outcome Measurements:	
A. COVID-19 testing data available through self-reported surveyB. COVID-19 vaccine data available through self-reported survey
Study Duration:	11 months – September 2022- August 2023

3. Study Design

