The ancillary study runs parallel with the larger ROSSEY RCT. Recruitment, enrollment, and baseline assessment are expected to last two months (September-November 2022). Enrolled participants will not receive the comic book and parent video series until after completion of the ROSSEY RCT Post 1 follow-up Survey to not bias the data of older siblings participating in the ROSSEY RCT. A follow-up assessment for Early Learning participants is anticipated to take place 10 months after the launch of recruitment (July-August 2023)

4. Sample size and power

Early Learning is an ancillary study of 50 participants. We will enroll and recruit participants for a total of eight weeks.

Enrollment Criteria

Parent/Guardian eligibility criteria for participation in the study include:

- Must have a child attending the Early Learning Program in the Yakima School District
- Must be able to provide informed consent and legal guardian assent either virtually, on the telephone, or in-person.
- Must have a permanent mailing address available for study staff to mail necessary materials OR a working email address.

5. Population and Data Source

Participants enrolled in the ROSSEY Study: 50 children and parents from the Yakima School District. Any participants subsequently found to be ineligible will be removed. The data sources for the primary analyses are COVID testing results received from the school administration and the survey data as entered in REDCap. The COVID vaccination status data is obtained through the parent and child surveys, completed in REDCap.

6. Presentation of analyses

For each of the continuous outcomes (including the primary outcome), the mean and standard deviation will be presented pre/post intervention and p value. For binary outcomes, the percentage and frequency of children in the outcome category of interest (e.g., percentage vaccinated) will be presented pre/post and p value.

7. Outcome Definitions

a. Primary Outcomes

The two co-primary outcomes of the trial are COVID-19 testing and COVID-19 vaccine uptake. COVID-19 data are captured through school testing and self-reported survey, and COVID-19 vaccine uptake data are captured through self-reported survey. All children and parent data will be included in the intention-to-treat analysis.

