COVID-19 testing: Health reports from the school are provided for the 2022-2023 school year that list positive covid test results of study participants with the date of testing and the school of attendance. Positive test results for COVID will be a binary, yes/no variable.

COVID-19 vaccine uptake: Parents are asked at enrollment to report their vaccination status and their child's vaccination status. At post survey, the parent is asked to report if they or their child have received any COVID-19 vaccine or booster since enrollment. Vaccination status will be a binary, yes/no variable.

b. Secondary Outcomes

Secondary outcomes for the trial include the following outcomes from the PROMIS – Pediatric and Parent Proxy Instruments. The PROMIS instruments used are Children's physical activity (PA), sleep, stress, depression, and anxiety. Parents' PA, sleep, stress, depression and anxiety. The final score is represented by the T-score, a standardized score with a mean of 50 and a standard deviation (SD) of 10.

The outcome measures will be collected at pre-and post-assessment.

8. Primary exposure definition

Receiving the educational materials: three comic books and two graphic motion videos.

9. Interim analysis plan

For this study, there was no interim analysis.

10. Multiple testing

We will adjust for multiple testing by controlling FDR.

11. Missing Data

We will inspect missing data mechanisms and the amount of missing data. We will conduct an additional sensitivity analysis with multiple imputations using multivariate imputation with chained equations (MICE) approach. We will report the amount of missing data and apply appropriate methods to account for the missing data.

12. Planned Statistical Analyses

a. Baseline Demographics

The baseline characteristics of enrolled participants will be summarized in a table.

b. Efficacy Analyses Overview

Pre/post-survey outcome analyses will be conducted after all participants have been contacted and the survey is closed with missing responses marked as loss to follow-up.

- 1) **Descriptive Analyses:** Positive COVID test results will be summarized by counts. Vaccine status and COVID testing results will be presented as counts and percentages. Continuous variables will be summarized by mean, standard deviation (SD), and median (IQR). Secondary outcomes will be compared using Chi-squared tests.

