- 2) **Primary Objectives:** The primary analysis of vaccine uptake and COVID testing will be conducted using a chi-squared test using $\alpha = 0.05$ and report pre/post changes over time.
- 3) **Secondary outcomes:** The secondary outcomes for the trial include measures from the PROMIS – Pediatric and Parent Proxy Instruments. The PROMIS instruments used are children's PA, sleep, stress, depression, and anxiety and parents' PA, sleep, stress, depression, and anxiety.

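### The co-primary outcome labelled COVID-19 testing is defined only as a positive result, so it does not measure the testing uptake named in the objective

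*SAP*

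**What the plan says.** The aim is stated as uptake. SAP section 2 (Primary Objectives) asks whether the materials "will increase COVID-19 testing and vaccine uptake in children", and Protocol section III also speaks of uptake of SARS-CoV-2 testing.

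SAP section 7a names COVID-19 testing as one of two co-primary outcomes. The detail under that name has two parts:

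- **Source:** "Health reports from the school are provided for the 2022-2023 school year that list positive covid test results of study participants", with date and school.
- **Variable:** "Positive test results for COVID will be a binary, yes/no variable".

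Other places describe the source differently:

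- SAP section 2 (Primary Outcome Measurements) names the self-reported survey alone.
- SAP section 5 names "COVID testing results received from the school administration and the survey data as entered in REDCap".
- The opening of SAP section 7a says "COVID-19 data are captured through school testing and self-reported survey".

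On analysis, SAP section 12b item 1 says "Positive COVID test results will be summarized by counts" and then lists COVID testing results separately, as counts and percentages. Item 2 says "The primary analysis of vaccine uptake and COVID testing will be conducted using a chi-squared test". Neither item says which variable enters that test.

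The Follow-up Survey paragraph of Protocol section VI lists the child's vaccination status and "SARS-CoV-2 mitigation behaviors and the secondary outcome measures". It does not name testing as an item.

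**The concern.** A positive result requires two things: the child was tested, and the test was positive. The education materials are meant to act on the first. The second depends largely on how much infection is circulating and on why children are tested. A yes/no variable built from a list of positives merges the two, and it places children who tested negative with children who were never tested.

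An analyst who applies the one written definition would therefore run a co-primary test on detected infection and report it under the heading of testing. A rise could reflect more testing or more infection. A null result would say almost nothing about uptake. A larger sample or a different test would not repair this, because the variable does not measure what the objective asks about.

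**Working it through.** **Text check.** The documents state no testing rate, effect size or power, so there is no planned figure to reproduce. I compared what SAP section 7a specifies for each co-primary:

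| Element | Vaccine uptake | COVID-19 testing |
|---|---|---|
| Asked before | Parent report at enrollment | Not stated |
| Asked after | Parent report of any dose since enrollment | Not stated |
| Source in the detail | Survey | School list of positives |
| Coded variable | Vaccinated yes/no | Positive yes/no |

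No section of either document defines a tested yes/no variable, a survey item for it, a recall window, or matching periods before and after.

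**What the coded variable estimates.**

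P(coded yes) = P(tested) × P(positive | tested)

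The objective concerns the first factor only.

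**Illustration of size.** The assumptions are mine except where noted:

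- 50 children at each time point. SAP section 4 gives 50; SAP section 2 and Protocol section IV say no size is defined.
- No dropout and no FDR adjustment.
- Before and after treated as independent samples, with an uncorrected 2×2 chi-squared test.
- Alpha 0.05, as in SAP section 12b item 2.
- Power by exact enumeration of two binomials.

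*Testing rises from 20% to 40%:*

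| Variable | Before | After | Power, n = 50 | Power, n = 40 |
|---|---|---|---|---|
| Any test | 20% | 40% | 0.595 | 0.497 |
| Positive, positivity 10% | 0.20 × 0.10 = 2% | 0.40 × 0.10 = 4% | 0.054 | 0.037 |
| Positive, positivity 20% | 0.20 × 0.20 = 4% | 0.40 × 0.20 = 8% | 0.118 | 0.116 |

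At 10% positivity the expected counts are 50 × 0.02 = 1 child before and 50 × 0.04 = 2 after.

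Pairing the same children does not change the picture. With McNemar's test at n = 50 and within-child correlation 0 to 0.4, power is 0.60 to 0.80 for any test. For a positive result it is 0.04 to 0.06 at 10% positivity and 0.12 to 0.15 at 20%.

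A second set of assumed rates agrees. For testing from 40% to 60%, a normal approximation gives power of about 52% for any test and 5% to 10% for a positive result at constant positivity of 5% to 20%.

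*Testing flat at 40% while positivity among the tested rises:*

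- Positivity 10% to 30%: coded rates 0.40 × 0.10 = 4% and 0.40 × 0.30 = 12%. The test is significant with probability 0.304.
- Positivity 10% to 40%: coded rates 4% and 0.40 × 0.40 = 16%. The probability is 0.539.

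Uptake has not changed in either case.

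*Opposite movement:* if testing rises from 40% to 60% while positivity falls from 10% to 5%, expected positives go from 50 × 0.40 × 0.10 = 2.0 to 50 × 0.60 × 0.05 = 1.5. The coded outcome falls although uptake rose.

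**The case against.** The strongest reply is that the plan does intend survey-measured testing. SAP section 2 names the survey as the source of this primary outcome, and SAP section 5 and the opening of section 7a also mention it. Protocol section III treats testing as one of the mitigation measures, and the follow-up survey covers mitigation behaviors, so a testing item may well have been fielded. SAP section 12b can be read as keeping positives descriptive and testing something else. The SAP is dated June 30, 2022, before the planned recruitment, so using the survey was not an afterthought.

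Much of this is fair. The survey was named in advance, and it cannot be said that the analyst would certainly test positives. But these lines name sources and reports; none defines a variable. They also disagree with each other and with the detail in section 7a, which is the only place a coding rule appears. The item, its coding and its window remain unspecified, and anyone who uses the survey must choose them outside the plan.

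It is also fair that the power figures rest on assumed rates, that McNemar's test is not the planned test, and that this is a small single-arm ancillary study. The figures illustrate the consequence. The mismatch between variable and objective needs no assumed rate.

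**Conclusion.** The concern holds. The only written definition of this co-primary measures detected infection, while the objective is testing uptake, and the plan does not say which variable enters the primary chi-squared test. As coded, a significant result in either direction does not answer the objective. Under the assumptions above, a doubling of testing that an any-test variable would detect about 60% of the time would be detected 5% to 12% of the time through positive results.

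The definition gap rests on the text alone. Only its numerical size depends on assumed testing and positivity rates and on 50 children per time point. Whether testing uptake can still be recovered depends on the survey forms, which are not in the documents. Because this is one of two co-primary outcomes, it must be corrected before analysis.

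**What to change.** 1. Check the fielded baseline and follow-up surveys for a testing item.
2. If the item is in both, define the co-primary as the child having had at least one SARS-CoV-2 test, of any result, in a fixed window (yes/no). Use the same item and window length before and after, from the survey source that SAP section 2 already names.
3. Make SAP sections 2, 5, 7a and 12b name that one variable and source. Report positive results descriptively as a separate outcome.
4. If there is no such item and baseline can no longer be collected (it was planned for September to November 2022, and the protocol is dated 1/03/24), relabel the outcome detected infection. Report it descriptively and state that testing uptake was not measured.
5. Use a school log of all tests, including negatives, only as supporting data, and only if it covers time after the intervention. The school reports in SAP section 7a cover 2022-2023, whereas the Risk Communication paragraph of Protocol section VI ties distribution to December 2023. Those dates must be reconciled first.

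**Cost.** If the item was fielded at both assessments, only SAP wording changes, and parent recall error is a small price. If it was not, a before/after comparison of testing uptake is probably out of reach, and the cost is giving up that co-primary claim.

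### SAP 7a gives no rule for building post-intervention vaccination status from two different survey questions, and the chi-squared test named for this co-primary outcome ignores that the same children are measured twice

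*SAP*

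**What the plan says.** SAP 7a names COVID-19 vaccine uptake as one of two co-primary outcomes and describes two survey items.

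- **Enrollment:** "Parents are asked at enrollment to report their vaccination status", and likewise their child's.
- **Follow-up:** "At post survey, the parent is asked to report if they or their child have received any COVID-19 vaccine or booster since enrollment".

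The only coding statement is "Vaccination status will be a binary, yes/no variable". SAP 5 adds "The COVID vaccination status data is obtained through the parent and child surveys, completed in REDCap".

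For binary outcomes, SAP 6 says that "the percentage and frequency of children in the outcome category of interest (e.g., percentage vaccinated) will be presented pre/post and p value". SAP 12b (Primary Objectives) states: "The primary analysis of vaccine uptake and COVID testing will be conducted using a chi-squared test", at a 0.05 level, with changes over time reported. SAP 12b (Efficacy Analyses Overview) starts the analysis once "the survey is closed with missing responses marked as loss to follow-up", and SAP 11 plans multiple imputation by chained equations (MICE) as a sensitivity analysis.

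On whose status counts, SAP 2 sets the primary objective in children, while SAP 7a says "All children and parent data will be included in the intention-to-treat analysis". Protocol VI (Follow-up Survey) describes the follow-up as updating the child's vaccination status.

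**The concern.** The enrollment item is cumulative: has this person been vaccinated by now? The follow-up item covers an interval: has there been any dose since then? They are not the same variable at two times, so a pre/post comparison needs a derivation rule, and none is given.

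Two codings are possible. The follow-up answer can be used directly, so that a child vaccinated before enrollment and not boosted moves from yes to no. Or baseline status can be carried forward, so that such a child stays yes. Two analysts following this SAP could therefore report different results for a co-primary outcome, in some circumstances with opposite signs.

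Settling on the second coding does not finish the matter. The same children then supply both percentages and can change in one direction only, while the named test is built for two independent groups.

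**Working it through.** **Inputs.** The plan states no vaccination rate, effect size or power for this outcome, so there is no figure to reproduce. SAP 4 and 5 give 50 participants (SAP 2 and Protocol IV say that no sample size is defined); I use n = 50 with no loss, for illustration. The following are assumptions: B = number of children vaccinated at baseline, N = 6 newly vaccinated, K = 4 boosted among those already vaccinated.

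**Step 1: the two codings.**

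- Follow-up answer used directly: change = (N + K − B)/n.
- Baseline carried forward: change = (B + N − B)/n = N/n.
- Difference, direct minus carry-forward: −(B − K)/n, the share vaccinated at baseline and not boosted.

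This is an identity, whatever the rates. The signs are opposite when N is at least 1 and N + K < B.

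**Step 2: range over assumed baselines (N = 6, K = 4).**

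| B | Direct | Carry-forward | Gap (points) |
|---|---|---|---|
| 8 | 16% to 20% | 16% to 28% | −8 |
| 10 | 20% to 20% | 20% to 32% | −12 |
| 15 | 30% to 20% | 30% to 42% | −22 |
| 20 | 40% to 20% | 40% to 52% | −32 |

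For B = 20, the direct post count is 6 + 4 = 10 of 50, the carry-forward count is 20 + 6 = 26 of 50, and the gap is (20 − 4)/50 = 16/50. With these inputs the sign reverses only when B exceeds 10; at 8 the rise is merely understated. Over a wider assumed range (baseline 10% to 60%, none to all of those boosted) the gap runs from 0 to −60 points.

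**Step 3: the named test under carry-forward.** Take B = 20, so 20/50 against 26/50. The uncorrected chi-squared test uses the pooled proportion 46/100 and a standard error of √(0.46 × 0.54 × 2/50) = 0.0997. Then z = 0.12/0.0997 = 1.20 and p = 0.23. But 20 of the 26 post positives are the same children as the 20 pre positives. The change is simply 6 of 50 children switching, and its standard error from within-child differences is √(0.12 × 0.88/50) = 0.046. The unpaired calculation more than doubles the standard error by counting baseline vaccination as noise twice.

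**Step 4: what carries the information.** Under carry-forward, only children unvaccinated at enrollment can change. With B = 20 that is 50 − 20 = 30 children, and 6/30 = 20.0% (exact Clopper-Pearson 95% CI 7.7 to 38.6). With B = 10 it is 6/40 = 15.0% (5.7 to 29.8).

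**The case against.** The strongest reply is that any sensible analyst would carry baseline forward. The outcome is labelled vaccination status in SAP 5 and 7a, SAP 6 speaks of the percentage vaccinated, the protocol describes the follow-up as an update, and the two items together are enough to derive status. This largely stands, and it is the better-supported reading. It does not supply the missing rule, and it leaves the unpaired test in place.

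A reader might infer more than the documents support:

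- **That the plan will report a spurious fall in vaccination.** The documents do not say that the follow-up answer will be used directly, and they give no baseline, new-dose or booster rate. The table shows what is possible, not what is likely. The term too low also presumes ever-vaccinated status as the target; that fits SAP 6, but the follow-up item itself counts boosters.
- **That loss to follow-up is ignored.** SAP 11 plans to inspect and report missing data and to run MICE. It does not say that the pre and post percentages must come from the same children.
- **That parent and child answers are merged.** SAP 7a's wording allows it, but the questionnaire is not in the documents and the protocol points to a child item.

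Nor is a paired significance test the natural replacement. When status cannot fall, a null of equal change in both directions is untrue as soon as one child is vaccinated. An estimate with an interval is more informative.

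**Conclusion.** The point holds and should be settled before analysis, because a co-primary variable has no derivation and its named test does not suit the data under the better-supported reading. Both findings follow from the text and need no assumed rate.

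The size is conditional. If the follow-up answer were used directly, the shortfall against the change in ever-vaccinated status is exactly the share vaccinated at baseline and not boosted: 32 points in the example with 20 of 50 vaccinated at baseline, 8 points with 8 of 50, and zero if everyone vaccinated at baseline is boosted. Under carry-forward there is no such bias, and the remaining fault is the independent-groups test. The documents do not support a claim that the reported result will in fact be biased downward.

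**What to change.** 1. **SAP 7a:** define the child's post status as yes if the child was vaccinated at enrollment or has had any dose since, using the child's own answer. Show pre and post percentages for the same followed-up children.
2. **SAP 12b and 6:** for this outcome, replace the unpaired chi-squared test and its p value with the number and proportion newly vaccinated among children unvaccinated at enrollment, with an exact 95% CI.
3. **Separate summaries:** report boosters in already vaccinated children, and parents' doses, as secondary summaries so that the primary denominator stays consistent.
4. **SAP 11:** keep the MICE sensitivity analysis for children lost to follow-up.
5. **Interpretation:** state that a single-arm estimate cannot separate an intervention effect from background uptake. State also that the since-enrollment window includes time before the materials were distributed, since both documents hold them back.

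**Cost.** Only SAP wording changes if child doses are recorded separately. The denominator shrinks and the interval widens, as in the 6/30 example, where it spans about 31 points (38.6 − 7.7). If the follow-up item does not separate child from parent, it would have to be split while the survey can still be changed. If the survey is already closed, a child-only outcome cannot be derived, and that must be reported.

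### SAP 7a does not settle whose vaccination defines the vaccine co-primary, so a parent's dose can count toward an endpoint stated for children

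*SAP*

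**What the plan says.** The primary objective in SAP section 2 asks whether the comic books and videos "will increase COVID-19 testing and vaccine uptake in children". The central hypothesis in the same table is wider: "students and parents who view the risk communications will be more likely to have increased COVID-19 testing and vaccine uptake".

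SAP section 7a gives the vaccine co-primary in three sentences. At baseline: "Parents are asked at enrollment to report their vaccination status and their child's vaccination status". At follow-up: "At post survey, the parent is asked to report if they or their child have received any COVID-19 vaccine or booster since enrollment". On the form of the variable: "Vaccination status will be a binary, yes/no variable". The opening paragraph of 7a, which covers both co-primaries, adds: "All children and parent data will be included in the intention-to-treat analysis".

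SAP section 6 says that for binary outcomes "the percentage and frequency of children in the outcome category of interest (e.g., percentage vaccinated) will be presented pre/post and p value". Under the Follow-up Survey heading, protocol section VI lists among the contents "child's COVID-19 vaccination status, and child's SARS-CoV-2 mitigation behaviors" and does not mention the parent's vaccination.

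SAP section 12b names a chi-squared test for the primary analysis of vaccine uptake and does not say whose uptake is tested.

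**The concern.** A co-primary endpoint should state whose event makes it positive. Here the objective names children, the follow-up wording joins parent and child with an 'or', the variable names nobody, and the analysis set names both. Under 7a alone, a family in which the parent had a booster and the child had nothing can be scored as a yes.

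Two consequences follow. First, two analysts working in good faith, one from section 6 and one from section 7a, could report different results for the same co-primary. Second, baseline is described as a report for each person and follow-up as a report for one or the other, so the before and after figures may not refer to the same person. If the question was fielded exactly as 7a words it, a yes cannot later be assigned to the child, and the child endpoint cannot be recovered from that item.

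This is separate from the change from vaccination status at baseline to doses since enrollment at follow-up, which would remain even if only the child were counted.

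**Working it through.** The documents give no vaccination rate, effect size or power for this endpoint, so there is no planned figure to reproduce. The check is a comparison of the texts, followed by an illustration with assumed rates.

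**Step 1. Whose vaccination does each place refer to?**

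| Place | Person |
|---|---|
| SAP 2, primary objective | Child |
| SAP 2, central hypothesis | Child and parent |
| SAP 6, binary outcomes | Child |
| SAP 7a, enrollment report | Parent and child, each |
| SAP 7a, follow-up report | Parent or child |
| SAP 7a, yes/no variable | Not stated |
| SAP 7a, analysis set | Child and parent |
| SAP 12b, primary test | Not stated |
| Protocol VI, follow-up survey | Child |

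The denominator is also open. SAP section 5 counts 50 children and parents together without saying whether that means pairs or persons.

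**Step 2. Readings left open.** (a) The child's own dose. (b) A dose in either member of the pair. (c) Parent and child records pooled as separate persons.

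**Step 3. How far the follow-up rate can differ.** Let c be the share of children and p the share of parents dosed after enrollment. Assume c = 0.10 and p = 0.30; neither figure is in the documents.

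- (a) c = 10%.
- (b) Lower bound max(c, p) = 30%; upper bound c + p = 40%; under independence 1 − (0.90 × 0.70) = 37%.
- (c) (0.10 + 0.30) / 2 = 20%.

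With p = 0.10 instead, (b) runs from 10% to 20%, with 1 − (0.90 × 0.90) = 19% under independence, and (c) gives 10%. The distortion of the follow-up rate depends on the assumed parent rate and can be nil.

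**Step 4. What this could do to the planned test.** Take 50 pairs and the chi-squared test that the SAP names. Whether that test suits paired data is a separate matter.

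- Child-only baseline of 10% (5/50); either-person follow-up with c = 0.10 and p = 0.20 under independence: 1 − (0.90 × 0.80) = 28% (14/50). Chi-squared = 100 × (5 × 36 − 14 × 45)² / (50 × 50 × 19 × 81) = 100 × 450² / 3,847,500 = 5.26, p = 0.022. With continuity correction: 100 × (450 − 50)² / 3,847,500 = 4.16, p = 0.041.
- Child-only at both times, with the child rate unchanged: 5/50 against 5/50, p = 1.
- Either-person at both times, with the parent rate 20% at each: 14/50 against 14/50, p = 1.
- Either-person at both times, with the parent rate 50% at baseline and 20% at follow-up: 1 − (0.90 × 0.50) = 55% before and 28% after, an apparent fall.

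With the child rate held at 10% throughout, the comparison can show a rise, no change or a fall, depending on who is counted and when.

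**The case against.** The strongest reply is that this is loose drafting, not a different endpoint. The statement that the variable is binary gives its type; it does not say that two answers are merged. Enrollment is described as two reports, so the follow-up sentence may be shorthand for two questions. SAP section 5 says vaccination status comes from both parent and child surveys, which fits separate capture. Section 6 uses the percentage vaccinated as its example of a figure reported for children, with a p value. The protocol's follow-up survey lists the child's status. The intention-to-treat sentence may be a general inclusion statement, since the study also has parent outcomes.

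Much of this stands. A reader might infer that the SAP sets an either-person rule, so that a parent-only booster will score as a yes, or that parent and child records will be pooled. The documents do not support either inference: no passage gives such a scoring or pooling rule, and the survey form is not available.

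The reply does not remove the inconsistency. Section 7a defines the endpoint, and nothing makes section 6 override it. The places that point to the child show the probable intention; they also show that the wording of 7a departs from it. The central hypothesis, which includes parents, keeps the other reading alive. A pre-specified co-primary should not depend on an unseen form to establish whose event it counts.

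**Conclusion.** The point holds as an inconsistency in the definition of a co-primary outcome. Section 7a conflicts with the primary objective, SAP section 6 and the protocol's follow-up survey, and its wording allows a parent's dose to count toward uptake in children. Because it could change the co-primary result, it should be resolved before analysis.

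Its size cannot be derived from the documents. At the assumed 10% for children and 30% for parents, a reader might infer that uptake is overstated by a factor of 3 to 4 (30% to 40% against 10%). That applies only to the follow-up rate, only under an either-person reading and only at those rates; the upper end also requires that no dosed child has a dosed parent. At 10% for parents the range starts at no distortion.

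Nor do the documents support a claim that the pre/post change is biased upward. The p value of 0.022 requires a child-only baseline set against an either-person follow-up, a pairing that no passage specifies, and the other combinations in the working give no change or a fall.

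**What to change.** In SAP sections 7a and 12b:

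- Define the vaccine co-primary as the child's own vaccination, with one record per child and the number of children as the denominator both before and after. State whether the 50 are pairs or persons.
- Record the parent's and the child's answers as separate variables at follow-up, as is described for enrollment.
- Replace the intention-to-treat sentence in 7a with one that assigns child data to the primary analysis and parent data to parent outcomes.
- Report parent vaccination as a separate, non-primary outcome, and align the central hypothesis in section 2 with this. The documents do not dictate this placement, but it follows the primary objective as written.
- If only a combined item was fielded, say so and limit the conclusion to any vaccination in the parent-child pair.

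The cost is a few sentences in the SAP and, if the follow-up question was a single item, splitting it in two. The drawback is fewer yes events in the primary analysis than under a combined reading.
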